9.7.1.6.1 PRIMARY EFFICACY ANALYSIS

Primary analysis of primary endpoint

The primary analysis will be based on MCI/Prodromal subjects from the FAS with the prespecified censoring rule applied. The primary endpoint is the change from baseline to 18 months in the derived ADCOMS. The dose-response of the primary endpoint is modelled with a first-order normal dynamic linear model, where Normal and Inverse-Gamma priors are used. The primary efficacy analysis will calculate the Bayesian posterior probability that the dose identified is the most likely ED_{90} dose that achieves 25% improvement over the placebo arm. At each interim analysis and the final analysis, 2 Bayesian probabilities will be summarized for each active dose: the probability it is the ED_{90} dose and the probability of achieving 25% improvement over the placebo arm.

For the clinical efficacy data (ie, derived ADCOMS, MMSE, CDR, ADAS-cog, CBB, ISLT, and FAQ) subjects will be censored at the time of initiation of treatment with AChEIs or memantine, if they were not on these medications at the time of Baseline cognitive assessment (Visit 2), and will be censored at the time of dose adjustment of AChEIs or memantine if they were already on stable treatment with these medications at the time of Baseline cognitive assessment (Visit 2). The value of the primary endpoint for censored subjects will be imputed using data up to the censoring time and Bayesian longitudinal modeling.

Sensitivity analysis of primary endpoint

After unblinding, the primary endpoint will be analyzed using the Bayesian methods described above as well as conventional statistical methods. The following additional Bayesian analyses will be conducted as sensitivity analyses:

- The primary endpoint will be analyzed regardless of initiation of treatment, or dose adjustment, with AChEIs or memantine using the same Bayesian analysis method as primary analysis. This is an intent-to-treat analysis without any censoring.
- In case of early success, the primary analysis as well as the above sensitivity analyses will be repeated after all subjects have completed 18 months of treatment or have been lost to follow-up.

Statistical methods for the final conventional analyses will use a mixed-effects model with repeated measures (MMRM) on the change from baseline in the derived ADCOMS at 18 months. The model will include treatment groups, randomization stratification variables (the presence or absence of ongoing treatment with AChEIs or memantine or both, and *ApoE4* status), and baseline ADCOMS as covariates. Other covariates such as adjusted hippocampal volume will be studied. These analyses will be performed as sensitivity analyses on the FAS as well as the PP set and as such, no multiplicity adjustments will be made to account for the interim analyses. In case of early success, the conventional analyses will also be performed using the data collected before the interim analysis.

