9.7.1.6 Efficacy Analyses

The MCI/Prodromal Cohort

The study in the MCI/Prodromal cohort is based on Bayesian adaptive design. Frequent interim analyses will be performed to assess the probability of early success and futility and to make early stopping decisions. Response adaptive randomization will be used to update the randomization probability among treatment groups at each interim analysis. Key definitions relevant to the Bayesian aspects of the adaptive design are given below.

Study Definitions

- **Maximum Effective Dose (d_{Max}):** The dose that achieves the greatest treatment effect.
- **ED₉₀:** The lowest dose that achieves at least 90% of the d_{Max} treatment effect in the derived ADCOMS.
- **Early Success:** The study in the MCI/Prodromal cohort will meet early success criteria if the probability that the ED₉₀ at 18 months of treatment achieves 25% improvement over placebo is at least 80%. Early success is achieved before all MCI/Prodromal subjects complete 18 months of treatment and can only be determined after at least 200 MCI/Prodromal subjects have been randomized. If early success is declared before full randomization, the randomization of new MCI/Prodromal subjects will stop but subjects already randomized into the study will receive the full 18 months of treatment (following confirmation from the Sponsor's Senior Management).
- **Futility:** The study in the MCI/Prodromal cohort will meet statistical futility criteria if the probability that the ED₉₀ is better than placebo by the clinically significant difference of 25% is less than 5% at 18 months of treatment. The statistical futility boundary is binding; if the statistical futility boundary is crossed the study will be considered to have failed.

- **Study Success:** The study in the MCI/Prodromal cohort will be considered a success if an ED_{90} at 18 months treatment has at least an 80% probability of achieving 25% improvement over placebo at either an interim analysis or at the final analysis.

The Mild to Moderate AD Cohort (revised per Amendment 01)

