E2609 is a novel, small-molecule BACE1 inhibitor. Preclinical studies have shown that after oral dosing, E2609 inhibits the production of $A\beta_{40}$ and $A\beta_{42}$ in brain (rat and guinea pig) and in cerebrospinal fluid (CSF) and plasma (rat, guinea pig, and monkey). In humans, E2609 has been shown to inhibit BACE1 enzyme activity in CSF and lower the levels of $A\beta$, including amyloid beta monomer from amino acid 1 to x ($A\beta_{[1-x]}$), $A\beta_{(1-40)}$ and $A\beta_{(1-42)}$, in CSF both in vitro and in vivo. See the Investigator's Brochure for additional information. The target indication for E2609 is therefore treatment and disease modification of AD.

The present clinical study represents the sole Phase 2 study for the E2609 program, and is designed to establish Proof of Concept in subjects with Mild Cognitive Impairment due to Alzheimer's Disease/Prodromal Alzheimer's Disease (referred to as MCI/Prodromal throughout the protocol). The study also allows investigation of efficacy in subjects with mild to moderate dementia due to Alzheimer's Disease (referred to as mild to moderate AD throughout the protocol) to determine whether the effects of E2609 in this later stage population are comparable with those established in the MCI/Prodromal population within

this same study. (revised per Amendment 01) In the MCI/Prodromal population, Bayesian response adaptive randomization design is used with frequent interim analyses to continually update randomization allocation based on emerging clinical endpoint data. This approach allows for ongoing assessment of drug futility or evidence of early success and can mitigate the risks associated with larger and longer studies required to demonstrate clinical efficacy by leading to more efficient study termination or early advancement to a Phase 3 program. Results from this study will guide both the decision to move into Phase 3 development and the selection of the dose strengths to be taken into Phase 3. Moreover, this study is intended to be supportive for registration in the MCI/Prodromal population.

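### After early success, the protocol ranks the complete 18-month refit as a sensitivity analysis and does not say which analysis supplies the reported effect and ED90

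*Protocol*

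**What the plan says.** Section 9.7.1.6 counts the MCI/Prodromal study a success if an ED90 dose "has at least an 80% probability of achieving 25% improvement over placebo at either an interim analysis or at the final analysis". Early success "can only be determined after at least 200 MCI/Prodromal subjects have been randomized"; the count is of subjects randomised, not subjects who have completed 18 months. Under Section 9.7.3 no further interim analyses follow early success, and subjects already randomised go on to complete 18 months of treatment.

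Section 9.7.1.6.1, under the heading for sensitivity analysis of the primary endpoint, introduces its list with "The following additional Bayesian analyses will be conducted as sensitivity analyses". The second item is: "In case of early success, the primary analysis as well as the above sensitivity analyses will be repeated after all subjects have completed 18 months". The synopsis and the second copy of Section 9.7.1.6.1 in the file say the same.

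The primary objective (Section 8.1) is to establish the ED90 on ADCOMS at 18 months. The Introduction (Section 7) adds: "Results from this study will guide both the decision to move into Phase 3 development and the selection of the dose strengths".

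**The concern.** The endpoint is the 18-month change. After early success, the analysis that contains every randomised subject's 18-month follow-up is given the lower rank, and the look that happened to cross is left as the primary one. A look is chosen as the crossing look because its posterior is high, so its effect estimate is biased upward. The dose picked there is picked on the same favourable data. If that estimate and dose are carried into Phase 3 planning, the effect is likely to be overstated and the dose choice may not survive the complete data. Leaving the reported analysis unnamed also allows a choice between two results once both are known.

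**Working it through.** **1. The plan's own figures.** Section 9.7.2.1 gives at least 90% probability of success in clinically meaningful scenarios and at most 5% false claims with 500 subjects. Neither can be reproduced. The protocol gives no placebo ADCOMS change, SD, prior parameters, longitudinal-model parameters, accrual rate or scenarios, and leaves the simulation plan to an SAP appendix.

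**2. Direction, without those inputs.** Crossing requires a posterior probability of at least 0.80 that slowing exceeds 25%. The posterior's 20th percentile is then at least 25%, and its median is higher. With an approximately normal posterior, mean ≥ 25% + 0.84 × posterior SD. The less information at the look, the larger the SD and the higher the estimate has to be.

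**3. Size, by simulation of the documented rules.**

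Inputs from the protocol:
- Looks at 100, 150, … 500 randomised, then every 3 months.
- Success at ≥ 0.80 from 200 randomised.
- Futility below 0.05.
- Decision on the most likely ED90 dose.

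Assumptions:
- Linear decline with random slopes and 3-monthly visits.
- 500 subjects accrued evenly over 24 months.
- Equal allocation, with no response-adaptive step.
- No dropout or censoring.
- SD/mean of the 18-month placebo change of 0.8 or 1.1.
- A sceptical dose-to-dose prior tuned to the stated 5%. Simulated false success was 0.044 at SD/mean 0.8 and 0.038 at 1.1.

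Results given early success (800 trials per row; estimates are median proportional slowing for the dose selected at crossing):

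| True slowing (3 doses) | SD/mean | At crossing | Complete data | Truth | Excess at crossing | Excess, complete | ED90 dose changes | Complete data miss the 80% rule |
|---|---|---|---|---|---|---|---|---|
| 15/20/25% | 0.8 | 0.424 | 0.308 | 0.227 | 0.197 | 0.081 | 31% | 57% |
| 15/20/25% | 1.1 | 0.428 | 0.337 | 0.229 | 0.199 | 0.108 | 24% | 51% |
| 20/30/30% | 0.8 | 0.437 | 0.351 | 0.290 | 0.147 | 0.061 | 33% | 33% |
| 20/30/30% | 1.1 | 0.435 | 0.365 | 0.294 | 0.141 | 0.071 | 26% | 41% |
| 20/30/40% | 0.8 | 0.461 | 0.392 | 0.364 | 0.097 | 0.028 | 26% | 19% |
| 20/30/40% | 1.1 | 0.457 | 0.406 | 0.370 | 0.087 | 0.036 | 23% | 26% |
| 30/40/50% | 0.8 | 0.518 | 0.473 | 0.454 | 0.064 | 0.019 | 34% | 4% |
| 30/40/50% | 1.1 | 0.504 | 0.480 | 0.461 | 0.043 | 0.019 | 27% | 9% |

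Excess is the estimate minus the truth. At crossing it is 4 to 20 points; on complete data it is 2 to 11. With a flat prior the excess at crossing was about 21 to 52 points in scenarios with a true effect, so the prior matters a great deal.

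**4. Observed 18-month data at the look.** In these runs crossing came at a median of 200 to 350 randomised, with a median of 0 subjects having an observed 18-month value. That depends on accrual, and the runs did not model the Stage A pause. Section 9.1.2.3 dates the study November 2014 to October 2019, about 59 months. With Stage B at about 42 months (synopsis), Stage B would start near month 59 − 42 = 17. Some of the 60 Stage A subjects, an unstated share of them MCI/Prodromal, could therefore have 18-month data by the 200-subject look.

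**The case against.** The strongest case on the other side is that little is missing. The primary analysis is repeated in full on complete data. Section 9.7.1.6.1 defines the primary output as two posterior probabilities per dose, not as a headline effect, and the SAP (not shown) may name the reported estimate. For the conventional MMRM, the pre-interim data set is described as an addition, which suggests that complete data are the default there. Ranking the refit as a sensitivity analysis also has a purpose: a prespecified rule, once met, is not re-adjudicated. Early advancement to Phase 3 is a stated aim of the design, and waiting for complete data takes time.

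Most of this stands, and it limits the point to status and reporting. It does not remove it, because the protocol itself assigns the lower rank and names no other source for the effect and ED90.

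Three stronger readings are tempting but not supported:
- **That the headline figures will come from the interim.** A reader might infer this from the ranking, but nothing in the protocol says so.
- **That any success estimate has a fixed floor.** With SD equal to the placebo change, weak priors and equal arms, 0.25 + 0.8416 × √(1.5625/n) gives 42%, 39% and 34% for n = 40, 60 and 125 outcomes per arm. The priors are not stated, the SD ratio is borrowed from the mild to moderate AD power statement, and allocation is adaptive. The n = 125 case is 500/4, so the floor argument also applies to success at the final look.
- **That the interim decision or the 5% error claim is wrong.** Nothing here shows that.

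**Conclusion.** The point holds as one of status and reporting. Once early success is declared, the protocol gives the best data on its own endpoint a subordinate rank and leaves the source of the reported effect and ED90 open. The upward direction of the bias at a crossing look is firm: it follows from the rule and appeared under every assumption tried. The size is illustrative. The figures of roughly 4 to 20 percentage points, and an ED90 change in about a quarter to a third of early-success trials, rest on the assumed SD ratio, prior, accrual and equal allocation, and cover scenarios with a true effect. The overstatement is small for strong effects and largest for weak ones. How far an interim at 200 randomised relies on modelled 18-month values cannot be settled from the protocol.

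**What to change.** In Section 9.7.1.6.1 and the synopsis:
- Keep the interim rule as the binding decision on success and on stopping randomisation, with the existing management confirmation.
- State that, after early success, the reported treatment effect, credible interval and ED90 come from the primary Bayesian model refitted to all randomised MCI/Prodromal subjects after 18 months. Move that item out of the sensitivity list.
- Report the interim posterior beside it as the decision record.

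The analysis is already planned, so the cost is wording. There are three downsides. The reported figure may be less favourable than the interim one or disagree with it. It arrives later, although Phase 3 planning may still start from the interim result. It reduces the upward bias without removing it, because the refit contains the interim data.

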9.7.1.6.2 SECONDARY EFFICACY ANALYSES

The MCI/Prodromal Cohort

An MMRM will be used to analyze the following secondary endpoint: (revised per Amendment 02)

- Change from baseline in total hippocampal atrophy at 12 and 18 months of treatment in MCI/Prodromal subjects as measured by vMRI

Comparisons between each treatment group and placebo will be performed.

The Mild to Moderate AD Cohort (revised per Amendment 01)

The MMRM will be used to analyze the change from baseline of derived ADCOMS at 18 months in mild to moderate AD. If there is no treatment group-by-population interaction in the overall study, the MMRM analysis will include all subjects (MCI/Prodromal or mild to moderate AD) in the overall study. Otherwise, the MMRM analysis will only include subjects in the Mild to Moderate AD cohort. The comparison between placebo and active doses will be performed within mild to moderate AD subjects regardless of subjects included in the MMRM analysis. Dunnett's method will be used to control for multiplicity due to multiple comparisons.

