9.7 Statistical Methods

All statistical analyses will be performed by the sponsor or designee. Statistical analyses will be performed using SAS software or other validated statistical software as required.

All statistical tests will be based on the 5% (2-sided) level of significance, except for the Bayesian methods on the primary endpoint.

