9.7.1.1.2 SECONDARY ENDPOINTS

Change from baseline in: (revised per Amendment 02)

- Total hippocampal atrophy at 12 and 18 months of treatment in MCI/Prodromal subjects as measured by vMRI
- The derived ADCOMS at 18 months of treatment in mild to moderate AD subjects (revised per Amendment 01)

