9.7.2 Determination of Sample Size

9.7.2.1 Sample Size Rationale in the MCI/Prodromal Cohort

Primary endpoint – derived ADCOMS

The sample size and design characteristics to test the hypothesis for the primary objective based on the primary endpoint, change from baseline of the derived ADCOMS at 18 months, were determined by means of simulations. Extensive study simulations have shown that a total of 500 subjects will be sufficient to demonstrate that the most likely ED₉₀ dose achieves a 25% improvement over placebo with a probability of at least 80% in the interim and final analyses. There is at least a 90% probability of study success for the dose response scenarios where treatment was considered to have a clinically meaningful treatment effect. Simulations have also shown that if there is no obvious dose effect, the probability of falsely claiming superiority to placebo is at most 5%.

For each of the 4 treatment groups (3 active doses and placebo) the final number of subjects per group will differ depending on the observed interim treatment responses. The simulation plan will be an appendix to the statistical analysis plan and will present further details.

vMRI

The null hypothesis is that there is no difference between active dose and placebo. There are 3 null hypotheses corresponding to 3 active doses. The alternative hypothesis is that at least 1 null hypothesis is false (1-sided). The null hypotheses will be tested using Dunnett's method with 1-sided alpha of 0.05. The statistical power was estimated through simulation for a moderate dose-response assumption that the percent reduction in change from baseline of total hippocampal volume compared with placebo would be 15%, 20%, and 25% corresponding to the 3 doses, respectively. The estimated power for the actual planned study sample size is 78% at 18 months assuming an attrition rate of 20% at 18 months. Under a stronger dose-response assumption (ie, the percent reduction in change from baseline of total hippocampal volume compared with placebo is twice as much as that in the moderate dose-response assumption), the estimated power is at least 99% at 18 months.

Amyloid PET

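### The MCI/Prodromal hippocampal-volume secondary has no deciding time point, and its analysis section omits the Dunnett test on which its power rests; with Dunnett at both 12 and 18 months the family-wise error is about 7–9.6%, not 5%

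*Protocol*

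**What the plan says.** Section 9.7.1.1.2 lists the secondary endpoint as "Total hippocampal atrophy at 12 and 18 months of treatment in MCI/Prodromal subjects as measured by vMRI", so two time points sit side by side and neither is ranked above the other.

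Section 9.7.1.6.2 analyses it by MMRM and adds that "Comparisons between each treatment group and placebo will be performed". No adjustment is named for this endpoint. Under the next subheading, the mild to moderate AD cohort is given Dunnett's method by name. The synopsis has the same wording.

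The vMRI paragraph of section 9.7.2.1 is more specific: "There are 3 null hypotheses corresponding to 3 active doses", and "The null hypotheses will be tested using Dunnett's method with 1-sided alpha of 0.05". The assumed slowing of volume loss "compared with placebo would be 15%, 20%, and 25% corresponding to the 3 doses, respectively". The result is stated for one time point: "The estimated power for the actual planned study sample size is 78% at 18 months", with 20% attrition.

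Section 9.7 sets the general level: "All statistical tests will be based on the 5% (2-sided) level of significance, except for the Bayesian methods on the primary endpoint".

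**The concern.** Three doses at two time points give six comparisons. The only multiplicity rule for this endpoint is in the sample-size section. It covers the doses, and no rule covers the two time points. A statistician working from 9.7.1.6.2 alone would not know to apply Dunnett, and the contrast with the AD cohort in the same section suggests that it is not needed. One working from 9.7.2.1 would apply Dunnett but could still call the endpoint positive at either time point, each at full alpha. The same two sections, read with 9.7, also leave open whether the test is 1-sided or 2-sided.

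This is the only secondary endpoint in the primary population. Section 9.2.5.4 uses it to back a disease-modification claim, and section 7 intends the study as supportive evidence for registration in this population. If the decision rule is open, results near the threshold can be read either way after the fact.

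**Working it through.** **1. Which test do the stated power figures rest on?**

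The 78% cannot be reproduced outright, because the protocol gives no mean or SD of hippocampal change. The amyloid PET calculation in 9.7.2.1 uses the same hypotheses and test and does give its inputs: SD 0.33, differences 0.15, 0.20 and 0.25, and 100 subjects over four arms, taken as 25 per arm. The any-dose power by simulation is:

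- Dunnett 1-sided 0.05 (critical value 2.09): 81.2%, against the stated 80%.
- Dunnett 2-sided 0.05 (critical value 2.39): 70.9%.

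So the PET figure rests on the 1-sided Dunnett test, as the text says.

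For vMRI, assume equal allocation of the planned 500: 500 × 0.8 / 4 = 100 evaluable per arm. Solving for the ratio of placebo mean change to SD that gives 78% under 1-sided Dunnett yields 1.44 (1.438 before rounding). The expected z for a dose is (proportional effect × 1.438) / √(2/100), which is 1.53, 2.03 and 2.54 for 15%, 20% and 25%. Doubling the effects then gives 99.96%, in line with the protocol's figure of at least 99%.

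**2. Family-wise error under each reading**

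Simulation with a shared placebo, equal arms, no effect at any dose or time, and an assumed correlation between the 12- and 18-month results. The protocol gives no correlation. Large-sample Dunnett critical values for three doses are 2.06 (1-sided 0.05) and 2.35 (2-sided 0.05).

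| Assumed correlation | Dunnett at each time, 1-sided | Dunnett at each time, 2-sided | Six unadjusted 2-sided 5% tests |
|---|---|---|---|
| 0.3 | 9.4% | 9.5% | 22.9% |
| 0.5 | 8.9% | 9.1% | 22.0% |
| 0.7 | 8.2% | 8.5% | 20.2% |
| 0.9 | 6.9% | 7.2% | 17.3% |

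A separate simulation gave 9.6% at correlation 0.3 for 2-sided Dunnett. Dunnett at 18 months only gives 5.0%. Three unadjusted 2-sided tests at one time point give 12.5%. Whatever the allocation, an exact 5% Dunnett test at each of two time points cannot exceed 2 × 5% = 10%.

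Adaptive randomization will make the arms unequal. This was checked for the unadjusted reading only: at 4:1:1:4 it gives 19–24% for correlations 0.9 to 0.5.

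**3. A result on which the sections disagree**

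Take one dose with a nominal 2-sided p of 0.045 in the favourable direction, so z ≈ 2.00. It exceeds 1.96 but falls short of both 2.06 and 2.35. It is significant if 9.7.1.6.2 is read as unadjusted, and not significant under either Dunnett version. The disputed zone is nominal 2-sided p from 0.039 to 0.05 under 1-sided Dunnett, and from 0.019 to 0.05 under 2-sided Dunnett.

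**4. Power under the possible repairs** (100 per arm, ratio 1.438)

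- 18 months decides, Dunnett 1-sided 0.05: 78%.
- 18 months decides, Dunnett 2-sided 0.05: 67.5%.
- Alpha split, 0.025 at each time point: 67% (1-sided) or 57% (2-sided) at 18 months.

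**The case against.** A reader might infer from 9.7.1.6.2 that this endpoint has no multiplicity rule and a false-positive rate of about one in five. The documents do not support that. Section 9.7.2.1 states a Dunnett test for exactly these three hypotheses in prescriptive terms, and 9.7.1.6.2 does not say that its comparisons are unadjusted. Silence in one section does not cancel a rule in another. The 17–23% needs that literal reading and is not the protocol's stated test. This part of the objection stands.

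It can also be argued that choosing the deciding time point is SAP detail. Section 9.7.1 defers further detail to an SAP that was not available here, study success rests only on the Bayesian ADCOMS criterion, and the trial is a Phase 2 proof-of-concept study. That lowers the stakes but does not remove the point. The protocol itself fixes two time points, a test for the doses, power at one time point, and two conflicting statements of sidedness.

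Finally, both scans measure change from the same baseline scan in the same person, so the correlation may be high and the excess small. At a correlation of 0.9 it is still about 7%.

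**Conclusion.** The point holds as an inconsistency in the protocol with a moderate inflation. The Dunnett test in 9.7.2.1 is missing from 9.7.1.6.2 and the synopsis, no time point is named as deciding, and 1-sided 0.05 in 9.7.2.1 contradicts 2-sided 5% in 9.7.

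Under the protocol's own Dunnett rule applied at both time points, the family-wise error is about 7–9.6% instead of 5%. This assumes equal arms and a 12-to-18-month correlation of 0.9 to 0.3. The figure of 17–23% describes only the literal unadjusted reading and should not be quoted as the error rate of the plan.

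The primary analysis and the stopping rules are not affected.

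**What to change.** In section 9.7.1.6.2 and the synopsis, state that:

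- the vMRI secondary is decided at 18 months, with the three dose–placebo comparisons from the MMRM adjusted by Dunnett's method;
- the 12-month comparisons are tested, Dunnett-adjusted, only for a dose that is significant at 18 months, or else are labelled supportive.

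State sidedness once. Either declare the 1-sided 0.05 in 9.7.2.1 as an explicit exception to 9.7, or use 2-sided 5% and restate the power.

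The time-point rule costs no stated power, because the 78% already assumes Dunnett at 18 months. It does mean that a 12-month-only result can no longer be called a positive secondary. Moving to 2-sided 5% lowers the stated power from 78% to about 67–68% under the assumptions above. Keeping 1-sided 0.05 preserves the 78%, but each direction is then tested at the level of a 10% 2-sided test, which should be said openly. Splitting alpha between the time points would also control the error, but at lower 18-month power than letting 18 months decide.

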All mild to moderate AD subjects will be included in the efficacy evaluations of the Mild to Moderate AD cohort. The analysis of the Mild to Moderate AD cohort is based on the group sequential design. Interim analyses in the Mild to Moderate AD cohort will only be performed after the MCI/Prodromal cohort crosses the early success boundary. The early efficacy signal based on the change from baseline of ADCOMS at 18 months is defined as crossing the interim-analysis boundaries for overwhelming efficacy in the mild to moderate AD population. The O'Brien-Fleming (OF) boundaries based on Lan-DeMets alpha spending function will be used to assess overwhelming efficacy. The corresponding OF boundaries based on P values will be 0.076, 0.0221, and 0.0423 for the first, second, and final analyses, respectively, according to 2 planned interim analyses at the 60% and 80% information fraction. (revised per Amendment 01)

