The null and alternative hypotheses and the statistical test are the same as those for vMRI. To estimate the sample size for the amyloid PET imaging subgroup at 18 months, a common SD of the change from baseline was estimated at 0.33 and a reasonable mean difference between treatment and placebo was estimated as 0.25 (standardized uptake value ratio [SUVR]). Assuming a moderate dose-response, the best dose would achieve a difference of 0.25 (SUVR) and the middle and low doses would achieve a difference of 0.2 and 0.15 (SUVR), respectively; this would require a total of 100 subjects from all 4 arms at 18 months to achieve 80% power.

9.7.2.2 Sample Size Rationale for the Mild to Moderate AD Cohort (revised per Amendment 01)

ADCOMS at Month 18

The null hypothesis is that there is no difference between active dose and placebo. There are 2 null hypotheses corresponding to 2 active doses. The alternative hypothesis is that at least 1 null hypothesis is false. The null hypotheses will be tested using Dunnett's test with 2-sided alpha of 0.05 as described for the Mild to Moderate AD cohort in [Section 9.7.1.6.2](#). The statistical power was estimated through simulation for the dose-response assumption that the percent reduction in change from baseline of ADCOMS at 18 months compared with placebo would be 33% and 50% corresponding to the 2 doses, respectively. The estimated power for the actual planned 200 mild to moderate AD subjects is approximately 80% assuming a 2-sided alpha of 0.05. (revised per Amendment 01)

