9.2.3 Rationale for the Use of Bayesian Adaptive Design

This study uses a Bayesian adaptive design for the MCI/Prodromal cohort only in Stage B. This design optimizes subject allocation and evaluation of efficacy in a smaller number of subjects by maximizing the number of subjects exposed to doses of interest. Frequent interim analyses will be performed to assess the probability of early success and futility and to aid in making early stopping decisions. Response adaptive randomization will be used to update the randomization probability among treatment groups at each interim analysis, such that subjects are more likely to receive a dose that is efficacious.

Subjects with mild to moderate AD will be assessed as a “nested” population that does not follow the Bayesian adaptive design. It was not considered appropriate to have a Bayesian design for both cohorts as this would have substantially increased the overall study sample size, delayed analyses of dose response, and would have added background “noise” for the

comparison of subjects with MCI/Prodromal AD compared with those with mild to moderate AD. Data from each cohort will be analyzed independently for the purposes of decision making. A separate analysis of the 2 cohorts avoids the risk of data from subjects with mild to moderate AD confounding the results for the primary population (MCI/prodromal). (revised per Amendment 01)

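### An interaction pre-test decides whether MCI subjects enter the AD-cohort ADCOMS model, and the protocol does not say whether the AD contrast then borrows the MCI effect

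*Protocol*

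**What the plan says.** Section 9.7.1.6.2 and the synopsis give the same rule for the mild to moderate AD cohort. An MMRM is fitted to change in ADCOMS at 18 months, and its population depends on a test: "If there is no treatment group-by-population interaction in the overall study, the MMRM analysis will include all subjects". Otherwise only AD subjects enter. The next sentence reads: "The comparison between placebo and active doses will be performed within mild to moderate AD subjects regardless of subjects included in the MMRM analysis". Multiplicity over the two doses is handled by Dunnett's procedure.

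Four other places bear on this.
- Section 9.2.3, on the two cohorts: "Data from each cohort will be analyzed independently for the purposes of decision making".
- Section 9.7.1.6, on timing: "Interim analyses in the Mild to Moderate AD cohort will only be performed after the MCI/Prodromal cohort crosses the early success boundary". Section 9.7.3 adds that an AD analysis is run if the MCI cohort is declared futile.
- Section 9.7: "All statistical tests will be based on the 5% (2-sided) level of significance", the Bayesian primary analysis excepted. No separate level is given for the interaction test.
- Section 9.7.2.2, on sample size: "The estimated power for the actual planned 200 mild to moderate AD subjects is approximately 80% assuming a 2-sided alpha of 0.05". The reductions assumed "compared with placebo would be 33% and 50% corresponding to the 2 doses, respectively".

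**The concern.** A test for interaction between a 200-subject cohort and a cohort of up to 500 has little power against realistic differences. A non-significant result is therefore weak evidence that the drug does the same in both populations, yet here it triggers pooling. What happens next depends on a model term that is not stated.

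- **Term dropped.** The model has one treatment effect per dose. The contrast for AD subjects is then the same number as the contrast for everyone, and is mostly MCI data.
- **Term kept.** The contrast rests essentially on AD data. MCI subjects contribute only to covariate slopes and the covariance structure, so the pre-test decides almost nothing.

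At stake is the question that sections 7 and 9.2.1 set for this cohort: whether the effect in later disease is comparable with that in MCI. A common-effect model assumes the answer. Dunnett's adjustment handles two doses and does not address a borrowed treatment effect.

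**Working it through.** **Inputs from the protocol.** AD: 200 subjects, 1:1:1 in Stage B, so about 67 per arm. MCI: up to 500, so 500/4 = 125 per arm if equal. Dunnett, two-sided 0.05, two doses. Interaction at 5% under the general rule in section 9.7.

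**Inputs assumed.** ADCOMS SD, placebo change and final MCI arm sizes are not given. MCI effects are therefore expressed as d, the difference from placebo in SD units, and varied from 0.15 to 0.8. Response-adaptive MCI allocation is represented by placebo/15 mg/50 mg sizes between 167/90/167 and 180/60/180.

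**The plan's own figure.** The 80% AD power cannot be reproduced without an SD. Solved backwards, it needs placebo change/SD = 1.02, so d = 0.33 x 1.02 = 0.34 and 0.50 x 1.02 = 0.51. As a check of method, the fully specified amyloid PET case (25 per arm, SD 0.33, differences 0.15/0.20/0.25, one-sided 0.05) gives 81.9% against the stated 80%.

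**Why the common-effect reading inflates error.** Take one dose with no AD effect and d = 0.34 in MCI, 125 per arm.
- SE of the interaction = sqrt(2/67 + 2/125) = 0.214. The true difference is 0.34/0.214 = 1.6 SEs, so it is usually missed.
- Weight of MCI in the pooled estimate = 125/(125 + 67) = 0.65. Expected pooled effect = 0.65 x 0.34 = 0.22.
- SE of the pooled effect = sqrt(2/192) = 0.102. Expected z = 0.22/0.102, about 2.2, against a Dunnett critical value of about 2.23.

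**Simulation.** No AD effect; 2-df interaction test at 5%. If it is not rejected, the pooled effect is used; otherwise the AD-only effect. Chance of declaring an AD effect, either direction:

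| MCI effect d (15/50 mg) | 125 per arm | Adaptive allocation |
|---|---|---|
| 0/0 | 6.7% | 6.7% |
| 0.15/0.15 | 18% | 21% |
| 0.20/0.25 | 30% | 38-41% |
| 0.25/0.34 | 41% | 50% |
| 0.33/0.33 | 44% | 50-51% |
| 0.34/0.51 | 40-41% | 40-41% |
| 0.50/0.50 | 34% | 33% |
| 0.60/0.60 | 20% | 18% |
| 0.80/0.80 | 6.5% | 6% |

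AD-only analysis, or a joint model keeping the interaction: about 5% in every row.

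Counting benefit-direction claims only, the mid-range rows give 28-48%, d = 0.15 gives 16-18%, d = 0.6 gives 16-17% and d = 0.8 gives 4%. The interaction test detected the difference in 18-31% of trials at d = 0.20/0.25 and 0.25/0.34, and in 57-61% at 0.34/0.51.

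**Sensitivity.**
- Interaction at 10%, 125 per arm: 31%, 37% and 24% at d = 0.25, 0.33 and 0.5.
- 20% attrition (stated for vMRI only): 30-41% for d = 0.25 to 0.5.
- MCI enrolment stopped early, benefit direction, MCI slowing of 20/25%, 25/35% and 33/50%: with 50 per arm 11%, 15% and 21%; with 75 per arm 16%, 24% and 30%.

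**Reverse case.** If the drug works in AD as assumed (33%/50%) but not in MCI, the same rule lowers AD power from about 80% to about 71%.

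**The case against.** The strongest answer is the sentence confining the comparison to AD subjects. Read plainly, the MCI treatment effect never enters the AD contrast, and error is about 5% whatever happens in MCI. That reading is available. A reader might infer that the plan carries a 30-50% false-claim rate outright; the documents do not support that, because they never state a common-effect model. The figure also depends on assumed effect and arm sizes and falls away at both ends of the range.

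Model terms may reasonably be left to the SAP, and a missing term alone would be no finding. The conditional pooling rule, however, is fixed in the protocol. Dropping a non-significant interaction is the usual reason to pre-test one, and the only MMRM terms listed (section 9.7.1.6.1, for the MCI cohort) include no interaction. It is fair that pooling with the term kept could still sharpen covariate slopes and the covariance, but that modest gain has no reason to hinge on an interaction test.

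A reader might also infer that AD interim looks are worse, because they follow MCI success and would borrow favourably selected data. Sections 9.7.1.6 and 9.7.3 do not say that the interims use the pooled model. The early-stopping runs above do not condition on MCI having crossed its boundary, which would raise their figures. No size is claimed for that effect.

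Finally, section 9.2.3 is mainly concerned with AD data confounding the MCI result, the opposite direction. If the AD contrast uses AD data only, the two sections can be reconciled; if a common effect is fitted, they cannot.

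**Conclusion.** The protocol fixes a data-dependent pooling rule that is either nearly idle or invalid, depending on a term it does not state, and it conflicts with the independence stated in section 9.2.3. With the treatment-by-population term kept, error stays near 5%. With it dropped, a drug effective only in MCI would be declared effective in AD in roughly 28-50% of trials for MCI effects of about 0.2-0.5 SD at full MCI enrolment. The chance is roughly 10-20% for smaller effects, effects near 0.6 SD or MCI enrolment stopped at 200 subjects, and 4-7% at 0.8 SD. These figures rest on an assumed range of MCI effects, assumed MCI arm sizes and an interaction test at 5%.

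This should be fixed. It concerns a secondary endpoint of a Phase 2 study and leaves the primary MCI analysis untouched, so it is not a reason to hold the trial.

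**What to change.** In section 9.7.1.6.2 and the synopsis, delete the interaction pre-test. State that the AD comparison, at interim and final analyses, comes from an MMRM in mild to moderate AD subjects only, with 15 mg and 50 mg each compared with AD placebo by two-sided Dunnett. A joint model that always keeps the treatment-by-population (by visit) term is an acceptable alternative. Report the interaction test and any common-effect model in all subjects as exploratory.

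The cost is two sentences, in both places. What is given up is precision borrowed from MCI; the stated 80% power is for 200 AD subjects and does not rely on it.
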